1. Confirm inclusion and exclusion criteria, including identifying a positive SARS-CoV-2 test
2. Subject informed consent (obtained before performing study related activities)
3. Randomization of eligible subject
4. Demographics
5. Medical history
6. COVID-19 symptoms
7. Record vital signs
8. Assessment of clinical status (COVID-19 7-point Ordinal Clinical Progression Outcomes Scale)
9. Record new medical conditions
10. Record concomitant medication
11. Adverse Event (AE) evaluation
12. Collection of data for later SOFA score calculation
13. Prior to study infusion, collect, process and store blood for SARS-CoV-2 antibody testing, which will be done at the central study laboratory.
14. C-reactive protein (CRP) measurement (record the results of a clinically obtained CRP performed within 24 hours prior to study product infusion; if a CRP was not obtained clinically, perform a CRP measurement by study protocol in the local clinical laboratory)
15. Complete Blood Count (CBC) and Complete Metabolic Panel (CMP) measurement (record the results of a clinically obtained CBC and CMP performed within 24 hours prior to study product infusion; if a CBC and/or CMP was not obtained clinically, perform them on study protocol in the local clinical laboratory)

Day 1 (Day of Transfusion)

1. Study Product Administration: 1 unit of convalescent plasma or Lactated Ringer's solution with multivitamins will be transfused. Study infusion will be monitored per site institutional transfusion policy.
2. Adverse Event (AE) evaluation

Day 2 (first calendar day after transfusion)

1. Record vital signs.
2. Assessment of clinical status (COVID-19 7-point Ordinal Clinical Progression Outcomes Scale)
3. Record new medical conditions
4. AE evaluation
5. Collection of data for later SOFA score calculation
6. CBC and CMP measurement (record the results of a clinically obtained CBC and CMP; if a CBC and/or CMP was not obtained clinically, perform them on study protocol in the local clinical laboratory if patient remains hospitalized)
7. If patient remains hospitalized, collect, process and store blood for SARS-CoV-2 antibody testing, which will be done at the central study laboratory.

Day 3-8 (Daily assessments only while patient hospitalized)

1. Record vital signs
2. Record new medical conditions
3. Assessment of clinical status (COVID-19 7-point Ordinal Clinical Progression Outcomes Scale)
4. AE evaluation (through Day 4 only)

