7.2 Assessments Between Hospital Presentation and Hospital Discharge

- Specimen type, date, and result of SARS-CoV-2 testing conducted clinically
- Date and time of study infusion

- COVID-19 7-point Ordinal Clinical Progression Outcomes Scale on every day of hospitalization (study Day 8, 15 and 29 by phone if participant is no longer hospitalized)
- SOFA on Day 2, if hospitalized
- Receipt of open label antivirals between enrollment and hospital discharge: hydroxychloroquine, remdesivir, lopinavir/ritonavir, other
- Receipt of open label immunomodulators between enrollment and hospital discharge
- Receipt of open label COVID-19 convalescent plasma
- Date of first receipt of supplemental oxygen (if applicable)
- Date of final receipt of supplemental oxygen (if applicable)
- Date of first receipt of high flow nasal cannula (if applicable)
- Date of final receipt of high flow nasal cannula (if applicable)
- Date of first receipt of non-invasive ventilation (if applicable)
- Date of final receipt of non-invasive ventilation (if applicable)
- Date of first receipt of invasive mechanical ventilation (if applicable)
- Date of final receipt of invasive mechanical ventilation (if applicable)
- Date of first receipt of extracorporeal membrane oxygenation (if applicable)
- Date of final receipt of extracorporeal membrane oxygenation (if applicable)
- Date of first receipt of vasopressors (if applicable)
- Date of final receipt of vasopressor (if applicable)
- Date of first ICU admission (if applicable)
- Date of final ICU discharge (if applicable)
- Date of hospital discharge (if applicable)
- Date of death (if applicable)
- Clinically obtained laboratory tests, including blood counts, chemistries, and CRP
- Safety assessments: myocardial infarction, ischemic stroke, deep venous thrombosis or pulmonary embolism, aspartate aminotransferase or alanine aminotransferase levels that are greater than twice the local upper limit of normal, stage II or greater acute kidney injury according to KDIGO creatinine criteria³⁹, receipt of new renal replacement therapy, transfusion reaction, transfusion related acute lung injury (TRALI), Transfusion associated cardiac overload (TACO), transfusion related infection. Definitions for each variable are detailed in the trials statistical analysis plan and are described for enrolling personnel in the trial manual of operations and/or electronic data capture system.

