8.7 Safety Outcomes and Adverse Events

The frequency and description of safety outcomes and adverse events will be reported. The association between intervention group and safety outcomes will be estimated without covariate adjustment. The following table lists the safety outcomes and the planned analyses (Table 3).

Table 3. Trial safety outcomes.		
Outcome	Type	Analysis
Receipt of renal replacement therapy	Binary	Risk difference
Documented venous thromboembolic disease (DVT or PE)	Binary	Risk difference
Documented cardiovascular event (myocardial infarction or ischemic stroke)	Binary	Risk difference
Transfusion reaction (fever/rash)	Binary	Risk difference
Transfusion related acute lung injury (TRALI)	Binary	Risk difference
Transfusion associated circulatory overload (TACO)	Binary	Risk difference
Transfusion related infection	Binary	Risk difference

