10.1.1 Potential risks of receiving convalescent plasma

One potential risk to receiving convalescent plasma is the possibility of developing antibody-mediated enhancement of infection (ADE). ADE can happen in the setting of viral and bacterial diseases and occurs when antibodies increase the severity of disease. ADE has been described in other types of coronaviruses, and it is also possible that antibodies to one type of coronavirus could enhance disease with another strain.⁴³ However, in the setting of MERS and the closely related SARS-CoV-1, evidence suggests that the use of convalescent plasma is safe.^{7,28,44} Anecdotal evidence of the use of convalescent plasma in COVID-19 also indicates that this is a safe treatment option.^{32,33} Another possible risk to receiving convalescent plasma is that the patient may mount a sub-optimal humoral immune response resulting in susceptibility to reinfection as has been seen with respiratory syncytial virus.⁴⁵ However, these concerns seem minor as compared to the possibility of limiting the duration and severity of disease, and avoiding interventions like mechanical ventilation, ARDS and sepsis. There are also risks associated with any transfusion of plasma including transmission of transfusion transmitted viruses (e.g. HIV, HBV, HCV, etc.), allergic transfusion reactions, anaphylaxis to transfusion, febrile transfusion reaction, transfusion related acute lung injury (TRALI), transfusion associated cardiac overload (TACO), and hemolysis should ABO incompatible plasma be administered. Another risk of plasma is thrombotic (clotting) complications, such as deep venous thrombosis, pulmonary embolism, myocardial infarction, and stroke. All study participants will be closely monitored for adverse events by study personnel.

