- Unexpected, in terms of nature, severity, or frequency, given the research procedures that are described in the protocol-related documents, such as the sIRB-approved research protocol and informed consent document; and the characteristics of the subject population being studied.
- Related or possibly related to participation in the research; possibly related means there is a reasonable possibility that the incident, experience, or outcome may have been caused by the procedures involved in the research.
- Suggests that the research places subjects or others at a greater risk of harm (including physical, psychological, economic, or social harm) than was previously known or recognized.

B.2. Determining Relationship of Adverse Events to Study Infusion or Study Procedures

Investigators will be asked to grade the strength of the relationship of an adverse event to study infusion or study procedures as follows:

- Definitely Related: The event follows: a) A reasonable, temporal sequence from a study procedure; and b) Cannot be explained by the known characteristics of the patient’s clinical state or other therapies; and c) Evaluation of the patient’s clinical state indicates to the investigator that the experience is definitely related to study procedures.
- Probably or Possibly Related: The event should be assessed following the same criteria for “Definitely Associated”. If in the investigator’s opinion at least one or more of the criteria are not present, then “probably” or “possibly” associated should be selected.
- Probably Not Related: The event occurred while the patient was on the study but can reasonably be explained by the known characteristics of the patient’s clinical state or other therapies.
- Definitely Not Related: The event is definitely produced by the patient’s clinical state or by other modes of therapy administered to the patient.

- Uncertain Relationship: The event does not meet any of the criteria previously outlined.

B.3. Clinical Outcomes that may be Exempt from Adverse Event Reporting

Study-specific outcomes of acute respiratory infection, COVID-19, and critical illness will be systematically collected for all patients in both study groups and are exempt from adverse event reporting unless the investigator considers the event to be Definitely Probably, or Possibly Related (or of an Uncertain Relationship) to the study infusion or study procedures. Examples of study-specific clinical outcomes include:

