- Death not related to the study procedures
- Neurological events
 - Ischemic stroke
- Cardiovascular events
 - Receipt of vasopressors
 - Cardiomyopathy
 - Myocardial infarction
 - Cardiac arrest
 - Deep vein thrombosis
 - Pulmonary embolism
- Respiratory events
 - Hypoxemia requiring supplemental oxygen
 - Acute respiratory distress syndrome
 - Receipt of mechanical ventilation
 - Receipt of extra-corporeal membrane oxygenation
- Gastrointestinal events
 - Elevation of aspartate aminotransferase or alanine aminotransferase
- Renal events
 - Acute kidney injury
 - Receipt of renal replacement therapy
- Hematologic or coagulation events
 - Neutropenia, lymphopenia, anemia, or thrombocytopenia

Note: A study-specific clinical outcome may also qualify as a reportable adverse event. For example, a cardiac arrest that the investigator considers Definitely or Possibly Related to the study infusion would be both recorded as a study-specific clinical outcome and reported as a Serious and Definitely or Possibly Related Adverse Event.

B.4. Decision tree for determining if an adverse event is reportable

Figure 2. Decision tree for determining if an adverse event is reportable

[figure not shown]

Figure adapted from Ranieri VM, Thompson BT, Barie PS et al. Drotrecogin alfa (activated) in adults with septic shock. N Engl J Med. 2012 May 31;366 (22):2055-64. PMID: 22616830.

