6.4 Outcomes with a competing risk of death

Some secondary outcomes, like the primary outcome, incorporate death as part of the scale. Others, such as length of hospital stay, do not. Because death censors length of stay, it is a competing outcome. Outcomes with a competing risk of death will be analyzed with a multi-state model. Both the instantaneous risk and cumulative risk of the outcome will be reported.

7 Safety Outcomes and Adverse Events

The frequency and description of safety outcomes and adverse events will be reported for all enrolled patients grouped by treatment assignment. The association between treatment received and safety

outcomes between groups will be estimated without covariate adjustment. The following table lists the safety outcomes and the planned analyses.

Outcome	Type	Analysis
Receipt of renal replacement therapy	Binary	Risk difference
Documented venous thromboembolic disease (DVT or PE)	Binary	Risk difference
Documented cardiovascular event (myocardial infarction or ischemic stroke)	Binary	Risk difference
Transfusion reaction	Binary	Risk difference
Transfusion related acute lung injury (TRALI)	Binary	Risk difference
Transfusion associated circulatory overload (TACO)	Binary	Risk difference
Transfusion related infection	Binary	Risk difference

8 Definition of the Primary Outcome

The primary outcome is patients' clinical status 14 days after randomization (measured on Study Day 15) as assessed with the seven-category COVID Ordinal Outcome Scale:

- Not hospitalized without limitation in activity
- Not hospitalized with limitation in activity
- Hospitalized not on supplemental oxygen
- Hospitalized on supplemental oxygen
- Hospitalized on non-invasive ventilation or high-flow nasal cannula
- Hospitalized on invasive mechanical ventilation or extracorporeal membrane oxygenation
- Death

While patients are in the hospital, primary outcome assessment will be performed by review of the electronic health records. For patients discharged prior to 14 days after randomization, study staff will call patients or their surrogates to obtain the patients' clinical status for primary outcome assignment.

9 Definition of SOFA Score

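### AST/ALT elevation is a named safety assessment with no SAP definition and no planned between-arm comparison, although its collection is the stated ground for exempting it from adverse event reporting

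*Protocol*

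**What the plan says.** Protocol 7.2 names as a safety assessment "aspartate aminotransferase or alanine aminotransferase levels that are greater than twice the local upper limit of normal". It then states: "Definitions for each variable are detailed in the trials statistical analysis plan", and adds that the manual of operations and/or the data capture system describe the variables for enrolling staff.

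Protocol 8.7 introduces its analyses with "The following table lists the safety outcomes and the planned analyses (Table 3"), and SAP section 7 with "The following table lists the safety outcomes and the planned analyses". Each table has seven rows. Neither has a row for liver enzymes, blood counts or any other laboratory value.

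Appendix B.3 gives examples of study-specific outcomes that may be exempt from adverse event reporting. They include "Elevation of aspartate aminotransferase or alanine aminotransferase", and also anemia, thrombocytopenia and other cytopenias. The reason given is that these outcomes "will be systematically collected for all patients in both study groups and are exempt from adverse event reporting". The exemption lapses when the investigator considers the event definitely, probably or possibly related, or of uncertain relationship.

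Protocol 5.1 obtains a CBC and CMP at baseline and again on Day 2, where "if a CBC and/or CMP was not obtained clinically, perform them on study protocol in the local clinical laboratory if patient remains hospitalized". On Day 8 results are recorded only if clinically available.

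Protocol 10.1.1 lists, among the risks of plasma, "hemolysis should ABO incompatible plasma be administered". Protocol 5.2 requires ABO-compatible plasma.

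**The concern.** Exempting expected events from individual reporting is sound when the same events are collected in both arms and then compared. The comparison takes the place of the case reports. Here the collection is promised and the exemption granted, but no comparison is planned.

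For transaminase elevation or anemia in patients hospitalized with COVID-19, case-by-case attribution is a weak detector. Appendix B.2 lets an investigator grade an event as probably not related when the patient's clinical state reasonably explains it, and Appendix B.3 classes these events as outcomes of acute respiratory infection, COVID-19 and critical illness. An increase over a background rate shows up in a count by arm and may not show up in any single case. Safety is a stated purpose of the trial (Protocol 3.1 and 11.2), and the final report as planned would give no by-arm result on a measure the protocol itself calls a safety assessment.

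**Working it through.** The documents give no figure to reproduce. The check is a cross-match of the safety assessments in Protocol 7.2 against the places where each should reappear. DVT and PE are counted as one item.

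| Assessment in Protocol 7.2 | Protocol 6.3 and SAP outcome list | SAP section 11 definition | Row in Table 3 and SAP section 7 |
|---|---|---|---|
| Myocardial infarction | yes | 11.4 | yes (shared row) |
| Ischemic stroke | yes | 11.4 | yes (shared row) |
| DVT or PE | yes | 11.3 | yes |
| New renal replacement therapy | yes | 11.2 | yes |
| Transfusion reaction | yes | 11.5 | yes |
| TRALI | yes | 11.6 | yes |
| TACO | yes | 11.7 | yes |
| Transfusion-related infection | yes | 11.8 | yes |
| Acute kidney injury, stage 2 or more | yes | 11.1 | **no** |
| AST/ALT above twice the limit | **no** | **no** | **no** |

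Of ten assessments, nine are listed and defined, and eight of those map to the seven analysis rows. AST/ALT is the only one that carries over nowhere. Acute kidney injury is listed and defined but has no analysis row.

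**Can an unattributed elevation reach the report another way?**

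- As an adverse event: Appendix B.3 exempts it, and Protocol Table 4 requires no record of a non-serious, unrelated event.
- As a safety outcome described by arm under SAP section 7: it is not on the list of safety outcomes.
- Through the Day 2 panel: the values may feed the Day 2 SOFA score, but no analysis of that score is planned.

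**Hemolysis.** It is not on the Appendix B.3 list; anemia is. It is not a listed safety outcome, and the transfusion-reaction criteria in SAP 11.5 contain no hemolysis or laboratory item.

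**What a comparison could show.** The documents give no event rates, so those below are assumptions. For rates p1 and p2 with n per arm:

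SE = √{[p1(1−p1) + p2(1−p2)] / n}; half-width of the 95% interval = 1.96 × SE; power ≈ Φ(|p2−p1|/SE − 1.96), two-sided 0.05.

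For 10% vs 16% and n = 500: SE = √[(0.0900 + 0.1344)/500] = 0.0212; half-width = 0.042; power = Φ(2.83 − 1.96) = 0.81.

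| Assumed rates | Half-width, n = 500 | Power, n = 500 | Half-width, n = 350 | Power, n = 350 |
|---|---|---|---|---|
| 5% vs 9% | 0.032 | 0.70 | 0.038 | 0.55 |
| 10% vs 16% | 0.042 | 0.81 | 0.050 | 0.66 |
| 20% vs 28% | 0.053 | 0.84 | 0.063 | 0.70 |

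The n = 350 columns assume that 70% of each arm contributes. They are there because 500 is an upper limit: patients already above the threshold at baseline cannot newly cross it, and the Day 2 draw covers inpatients only.

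**The case against.** A reader might infer that liver injury and hemolysis would go unreported altogether, or that both are exempt. The documents do not support that. Hemolysis is not on the exempt list. A related or uncertain event goes on the adverse event form whether or not it is serious (12.3). Serious events within 72 hours of infusion are to be reported regardless of cause (Appendix B), although the text does not say how that rule and the exemption combine for a serious event on the exempt list. Concerns about a transfusion reaction go to the blood bank or follow institutional policy (5.5), and a suspected reaction that stops the infusion must be reported (5.6). Adverse event frequencies are reported by assigned group, and the DSMB reviews clinical outcomes at the interim analyses. The hemolysis risk in 10.1.1 is also conditional on ABO-incompatible plasma, which 5.2 rules out. All of this stands, and it limits the point to events judged unrelated.

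It can also be said that an assessment is not an outcome, that 7.2 already states the threshold, that the manual of operations may say more, and that 10.1.1 does not name liver injury as a risk of plasma. The last is correct and lowers the stakes. The first does not explain the gap, since the other nine assessments in the same sentence all became listed and defined outcomes. A stated threshold is not a full definition either: time window, baseline status and denominator are open. A manual for enrolling staff would not supply a planned analysis.

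Finally, laboratory tests after Day 2 are clinically driven, and bedside staff who give the product are not blinded (4.7), so a later count could reflect differential testing. That is a reason to make Day 2 the main time point, and no reason to omit the comparison.

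**Conclusion.** The point holds in a limited form. AST/ALT elevation is designated a safety assessment, its promised SAP definition is absent, and it has no planned comparison, while its systematic collection is the ground for exempting it from adverse event reporting. For elevations and blood-count falls judged unrelated, planned by-arm comparisons number zero, so a modest excess under plasma could be missed. For hemolysis the gap is smaller: it is reportable, but as a named risk it has no listed outcome and no criterion in SAP 11.5.

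The precision figures show only that a comparison would be informative for differences of several percentage points. They rest on assumed rates and will be somewhat optimistic at 500 per arm. The point also assumes that the CMP includes AST, ALT and bilirubin; the documents do not list its components. The primary analysis is not affected.

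**What to change.** 1. Add AST or ALT above twice the local upper limit of normal to Protocol 6.3 and Table 3, and to the SAP outcome list, section 7 and section 11, as a binary outcome with a risk difference by assigned group. State the grouping explicitly, because SAP section 7 reports frequencies by assignment but speaks of treatment received for the association.
2. Make the Day 2 CMP the main time point, and take baseline status into account, for example by reporting patients below and above the threshold at baseline separately. Label any count from later tests as clinically driven.
3. Add a descriptive by-arm summary of Day 2 CBC and CMP values, at least hemoglobin and bilirubin, adjusted for the baseline value. Note it as an exception to the rule that safety comparisons are unadjusted.
4. State in the SAP how hemolysis is captured.
5. Reconcile Protocol 7.2 with the safety tables, including a row for acute kidney injury.

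The cost is wording and a few table rows, with no new data collection. Two limits remain: Day 2 covers only about the first day after infusion, and precision will fall somewhat short of that with 500 per arm.

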7.3 Assessments Following Hospital Discharge

7.3.1 Acute Care Follow-up

For participants discharged to home or a post-acute care facility (e.g., long term acute care facilities, skilled nursing facilities, or acute rehabilitation facilities) prior to the Day 8, Day 15 or Day 29 assessment, we will perform these assessments via telephone follow-up. The Day 8 call window will be Day 8 through 14. The Day 15 call window will be Day 15 through 22. The Day 29 call window will be Day 29 through 36. During these telephone calls, we will interview the patient, LAR, or facility staff to assess:

- Date of death (if applicable)
- ED visits and hospital readmissions after hospital discharge
- Location at the time of the call (home, long term acute care facility, skilled nursing facility, acute rehabilitation facility, hospital)
- Selected non-laboratory safety outcomes after hospital discharge
- COVID-19 7-point Ordinal Clinical Progression Outcomes Scale

The follow-up period for vital status (dead versus alive) is through Study Day 29. For most patients, we will establish vital status during the Study Day 29 visit (either in person for those who remain in the hospital or by phone for those who have been discharged). For patients who are not reached for the Study Day 29 visit, we will seek to establish vital status via phone calls, emails, and searches through medical records, obituaries, social media, and other sources.

